5.2 Rationale for the Present Study

This study will evaluate the efficacy and safety of VX-445 in TC with TEZ/IVA in subjects with CF who are heterozygous for *F508del* (F) and a second *CFTR* allele carrying a minimal function (MF) mutation that is non-responsive to TEZ, IVA, or TEZ/IVA (refer to [Appendix A](#) for MF mutations). Patients with this genotype (F/MF) usually have severe disease and lack approved CFTR modulator therapy; previous studies with TEZ/IVA (Study VX14-661-107) and LUM/IVA (Study VX09-809-102) failed to demonstrate efficacy in this patient population. Due to this high unmet need, VX-445 is being developed in TC with TEZ/IVA for F/MF subjects. The potential for benefit in these patients is supported by in vitro data and clinical data in F/MF

subjects; in addition, the TC of VX-445/TEZ/IVA is generally safe and well tolerated (refer to VX-445 Investigator's Brochure).

6 STUDY OBJECTIVES

6.1 Primary Objective

To evaluate the efficacy of VX-445 in TC with TEZ and IVA in subjects with CF who are heterozygous for *F508del* and a minimal function mutation (F/MF subjects)

6.2 Secondary Objectives

- To evaluate the safety of VX-445 in TC with TEZ and IVA
- To evaluate the pharmacodynamics (PD) of VX-445 in TC with TEZ and IVA
- To evaluate the pharmacokinetics (PK) of VX-445, TEZ, and IVA when administered in TC

7 STUDY ENDPOINTS

7.1 Primary Endpoint

Absolute change in ppFEV₁ from baseline at Week 4

7.2 Secondary Endpoints

7.2.1 Key Secondary Endpoints

- Absolute change in ppFEV₁ from baseline through Week 24
- Number of pulmonary exacerbations (PEX) through Week 24
- Absolute change in SwCl from baseline through Week 24
- Absolute change in Cystic Fibrosis Questionnaire – Revised (CFQ-R) respiratory domain score from baseline through Week 24
- Absolute change in body mass index (BMI) from baseline at Week 24
- Absolute change in SwCl from baseline at Week 4
- Absolute change in CFQ-R respiratory domain score from baseline at Week 4

7.2.2 Other Secondary Endpoints

- Time-to-first PEX through Week 24
- Absolute change in BMI z-score from baseline at Week 24
- Absolute change in body weight from baseline at Week 24
- Safety and tolerability assessments based on adverse events (AEs), clinical laboratory values, ECGs, vital signs, and pulse oximetry
- PK parameters of VX-445, TEZ, M1-TEZ, and IVA

8 STUDY POPULATION

Eligibility will be reviewed and documented by an appropriately qualified member of the investigator's team before subjects are randomized.

Subjects who meet all of the inclusion criteria and none of the exclusion criteria will be eligible.

8.1 Inclusion Criteria

1. Subject (or his or her legally appointed and authorized representative) will sign and date an informed consent form (ICF), and, when appropriate, an assent form.
2. Willing and able to comply with scheduled visits, treatment plan, study restrictions, laboratory tests, contraceptive guidelines, and other study procedures.
3. Age 12 years or older, on the date of informed consent.
4. Confirmed diagnosis of CF as determined by the investigator.
5. Heterozygous for *F508del* and an MF mutation (F/MF genotypes, see [Appendix A](#) for eligible MF mutations). If the screening *CFTR* genotype result is not received before randomization, a previous *CFTR* genotype laboratory report may be used to establish eligibility. Subjects who have been randomized and whose screening genotype does not confirm study eligibility must be discontinued from the study ([Section 9.9](#)).
6. Forced expiratory volume in 1 second (FEV₁) value $\geq 40\%$ and $\leq 90\%$ of predicted mean for age, sex, and height (equations of the Global Lung Function Initiative [GLI])⁹ at the Screening Visit. Spirometry measurements must meet American Thoracic Society/European Respiratory Society criteria¹⁰ for acceptability and repeatability.
7. Stable CF disease as judged by the investigator.
8. Willing to remain on a stable CF treatment regimen (as defined in [Section 9.5](#)) through completion of study participation.

8.2 Exclusion Criteria

1. History of any illness or any clinical condition that, in the opinion of the investigator, might confound the results of the study or pose an additional risk in administering study drug(s) to the subject. This includes, but is not limited to, the following:
 - Clinically significant cirrhosis with or without portal hypertension
 - Solid organ or hematological transplantation.
 - Alcohol or drug abuse in the past year, including, but not limited to, cannabis, cocaine, and opiates, as deemed by the investigator.

- Cancer, except for squamous cell skin cancer, basal cell skin cancer, and Stage 0 cervical carcinoma in situ (all 3 with no recurrence for the last 5 years)
2. Any of the following abnormal laboratory values at screening:
 - Hemoglobin <10 g/dL
 - Total bilirubin $\geq 2 \times$ ULN
 - Aspartate transaminase (AST), alanine transaminase (ALT), gamma-glutamyl transferase (GGT), or alkaline phosphatase (ALP) $\geq 3 \times$ ULN
 - Abnormal renal function defined as glomerular filtration rate ≤ 50 mL/min/1.73 m² (calculated by the Modification of Diet in Renal Disease Study Equation)^{11,12} for subjects ≥ 18 years of age and ≤ 45 mL/min/1.73 m² (calculated by the Counahan-Barratt equation)¹³ for subjects aged 12 to 17 years (inclusive)
 3. An acute upper or lower respiratory infection, PEx, or changes in therapy (including antibiotics) for sinopulmonary disease within 28 days before the first dose of study drug (Day 1).
 4. Lung infection with organisms associated with a more rapid decline in pulmonary status (including, but not limited to, *Burkholderia cenocepacia*, *Burkholderia dolosa*, and *Mycobacterium abscessus*). For subjects who have had a history of a positive culture, the investigator will apply the following criteria to establish whether the subject is free of infection with such organisms:
 - The subject has not had a respiratory tract culture positive for these organisms within the 12 months before the date of informed consent.
 - The subject has had at least 2 respiratory tract cultures negative for such organisms within the 12 months before the date of informed consent, with the first and last of these separated by at least 3 months, and the most recent one within the 6 months before the date of informed consent.
 5. An acute illness not related to CF (e.g., gastroenteritis) within 14 days before the first dose of study drug (Day 1).
 6. Ongoing or prior participation in a study of an investigational treatment within 28 days or 5 terminal half-lives (whichever is longer) before screening. The duration of the elapsed time may be longer if required by local regulations.
 7. Use of prohibited medications as defined in [Table 9-2](#), within the specified window before the first dose of study drug (Day 1).
 8. Pregnant or nursing females. Females of childbearing potential must have a negative pregnancy test at screening (serum test) and Day 1 (urine test).
 9. The subject or a close relative of the subject is the investigator or a subinvestigator, research assistant, pharmacist, study coordinator, or other staff directly involved with the conduct of the study at that site. However, an adult (aged 18 years or older) who is a relative of a study staff member may be randomized in the study provided that
 - the adult lives independently of and does not reside with the study staff member, and

[figure not shown]
- the adult participates in the study at a site other than the site at which the family member is employed.

9 STUDY IMPLEMENTATION

9.1 Study Design

This is a Phase 3, randomized, double-blind, placebo-controlled, parallel-group, multicenter study. A schematic of the study design is shown in Figure 9-1.

Figure 9-1 Schematic of the Study Design

IVA: ivacaftor; N: number of subjects; TEZ: tezacaftor

Notes: The figure is not drawn to scale. The Safety Follow-up Visit is not required for subjects who complete the Week 24 Visit and enroll in an open-label study within 28 days after the last dose of study drug (Section 9.1.3).

Study drug is defined in Section 10.

Approximately 360 subjects will be randomized (1:1) to the TC VX-445/TEZ/IVA arm or the triple placebo arm. The planned dosages to be evaluated are shown in Table 9-1. Randomization will be stratified; details are provided in Section 9.2.

Table 9-1 Treatment Arms and Dosages

Treatment Arm	VX-445 Dosage	TEZ Dosage	IVA Dosage
TC	200 mg qd	100 mg qd	150 mg q12h
Triple placebo	0 mg	0 mg	0 mg

IVA: ivacaftor; q12h: every 12 hours; qd: once daily; TC: triple combination; TEZ: tezacaftor

Note: Study drug administration is described in Section 9.6.

Study visits and assessments to be conducted are shown in Table 3-1 and Table 3-2. All visits will occur within the windows specified.

9.1.1 Screening

The Screening Period (Day -28 through Day -1) will occur within 28 days before the first dose of study drug.

Screening assessments will be used to confirm that subjects meet the eligibility criteria. The investigator (or an appropriate authorized designee) will obtain informed consent and assent, if applicable, from each subject before any study procedure takes place.

9.1.1.1 Repetition of Screening Assessment(s)

Screening assessments may be repeated once to establish study eligibility. If repeat values of the individual assessment(s) are within the eligibility criteria and completed within the screening window, then the subject is eligible for the study.

9.1.1.2 Rescreening

Subjects may be rescreened once. If a subject is rescreened, all screening assessments will be repeated, except for:

- *CFTR* genotyping
- Follicle-stimulating hormone (FSH) level (if serum FSH level was in the postmenopausal range as determined by the laboratory performing the test during prior screening)
- G6PD activity test
- Ophthalmologic examination (if performed within 3 months of the date of informed consent, for subjects <18 years of age)

If a subject is rescreened, a new screening window will begin when the first rescreening assessment has been initiated.

9.1.1.3 Extension of Screening Period Window

A subject may have the Screening Period window extended by 2 weeks for the following reasons:

- Repetition of the Screening Period assessments (Section 9.1.1.1)
- Unexpected operational or logistic delays, or to meet the eligibility criteria
- Scheduling of ophthalmologic examination (for subjects <18 years of age on the date of informed consent, [Section 11.7.6](#))
- 28-day washout period for subjects who have been on an investigational or commercially available *CFTR* modulator (e.g., TEZ/IVA, IVA [Kalydeco], LUM/IVA [Orkambi]; see [Table 9-2](#)).

9.1.2 Treatment Period

The Treatment Period will be randomized, double-blind, and placebo-controlled. It will last approximately 24 weeks (Day 1 through Week 24). Study drug administration details are provided in [Section 9.6](#).

Randomization will occur before the first dose of study drug during the Treatment Period and may occur on either Day 1 or Day -1. Randomization and stratification details are provided in [Section 9.2](#).

Subjects who prematurely discontinue study drug treatment will remain in the study from the time of discontinuation of study drug treatment through the last scheduled study visit and complete the assessments for all study visits, as described in Section 9.1.3.

9.1.3 Follow-up

The Safety Follow-up Visit will occur approximately 28 days after the last dose of study drug for subjects who complete study drug dosing and for subjects who prematurely discontinue study drug dosing, as described in Section 9.1.4.

An open-label study will be available for subjects who complete the Week 24 Visit and are eligible. The Safety Follow-up Visit is not required for subjects who complete the Week 24 Visit and enroll in an open-label study within 28 days after the last dose of study drug.

9.1.4 Early Termination of Treatment

If a subject prematurely discontinues study drug treatment, an Early Termination of Treatment (ETT) Visit should be scheduled as soon as possible after the decision to discontinue treatment. Subjects who prematurely discontinue treatment will also be required to complete the Safety Follow-up Visit, approximately 28 days after their last dose of study drug. The assessments performed at the Safety Follow-up Visit are listed in [Table 3-2](#).

If the ETT Visit occurs 3 weeks or later following the last dose of study drug, then the ETT Visit will replace the Safety Follow-up Visit, and a separate Safety Follow-up Visit will not be required.

Subjects who prematurely discontinue study drug treatment will continue to complete all scheduled study visits for assessments following completion of the ETT Visit, as detailed in [Table 3-2](#). Data regarding concomitant antibiotic therapy for sinopulmonary signs/symptoms will also continue to be collected for these subjects.

If a subject withdraws from the study and also withdraws consent or assent, no further assessments will be performed. Vertex may retain and continue to use any data and samples collected before such withdrawal of consent or assent.

9.1.5 Lost to Follow-up

A subject will be considered lost to follow-up if both of the following occur:

- The subject misses 2 consecutive study visits (telephone contact and/or clinic visit) and is subsequently unable to be contacted by telephone (3 documented attempts by telephone within 2 weeks following the second missed visit)
- The subject does not respond within 2 weeks to a registered letter sent after the 3 attempted telephone contacts.

9.1.6 Completion of Study Participation

Completion of study participation for each individual subject is defined as one of the following:

- For subjects who complete the Treatment Period and enter an open-label study within 28 days of the Week 24 Visit: the Week 24 Visit
- For subjects who complete the Treatment Period and do not enter an open-label study within 28 days of the Week 24 Visit: the Safety Follow-up Visit
- For subjects who prematurely discontinue study drug treatment but do not withdraw consent (and assent, as applicable): the latest of the Week 24 Visit, ETT Visit, or Safety Follow-up Visit (if required)
- For subjects who withdraw consent or assent: date of withdrawal of consent or assent, whichever is earlier ([Section 9.9](#))

If subjects are lost to follow-up ([Section 9.1.5](#)), the date of completion of study participation will be defined as the date of the last contact.

The end of study is defined in [Section 13.2.8](#).

9.1.7 Independent Data Monitoring Committee

This study will be monitored by an independent data monitoring committee (IDMC), which will conduct periodic planned safety review(s) of study data and the planned efficacy interim analysis (IA) ([Section 12.3.6.2](#)). Procedural details of the IDMC structure and function, frequency of meetings, and data planned for review will be included in the IDMC charter. The IDMC charter will be finalized before the first subject is screened.

9.2 Method of Assigning Subjects to Treatment Groups

Subjects will be randomized (1:1) to the TC VX-445/TEZ/IVA arm or to the triple placebo arm. Randomization will be stratified by ppFEV₁ determined during the Screening Period (<70 versus ≥70), age at the Screening Visit (<18 versus ≥18 years of age), and sex (male versus female).

An interactive web response system (IWRS) will be used to assign subjects to treatment. The randomization code list will be produced by Vertex Biometrics or a qualified randomization vendor.

9.3 Rationale for Study Design and Study Drug Regimens

9.3.1 Study Design

This Phase 3 study will assess the efficacy, safety, PD, and PK of VX-445/TEZ/IVA TC therapy in subjects with CF who have F/MF genotypes.

A randomized, double-blind, controlled study design was selected to ascertain the effects of VX-445/TEZ/IVA while avoiding observer bias. Placebo is considered the appropriate comparator because efficacy has not been established for a corrector, potentiator, or any corrector/potentiator combination in subjects with F/MF genotypes.

This study will have a 24-week treatment duration to allow for the collection of placebo-controlled safety data for this duration and the collection of data for outcomes that require longer treatment durations to demonstrate an effect (e.g., PEx and changes in nutritional status).

The primary endpoint is the absolute change in ppFEV₁ at Week 4. Previous studies of CFTR modulators (IVA, LUM/IVA, and TEZ/IVA) have demonstrated that efficacy related to lung

function (ppFEV₁) can be reliably established using an endpoint at Week 4. In these studies, rapid improvements in ppFEV₁ are observed by Day 15, with a separation between the active treatment and placebo groups that is sustained through 24 weeks of treatment. These studies were conducted in patients with different genotypes, baseline ppFEV₁, and age groups, using CFTR modulators that had different magnitudes of response.

9.3.2 Study Drug Dose

VX-445 Dosage

A VX-445 dose of 200 mg qd was selected for the current study based on an assessment of the benefit-risk profile from the Phase 2 Study VX16-445-001 (Study 445-001) Part D, which evaluated a range of VX-445 doses (50 mg qd, 100 mg qd, and 200 mg qd) in TC with TEZ/IVA for 4 weeks in subjects with F/MF genotypes. The TC was generally safe and well tolerated in all VX-445 dose groups, and F/MF subjects who received the VX-445 200 mg qd TC demonstrated a clinically meaningful improvement in ppFEV₁ (within-group mean [SE] absolute change of 13.8 [1.4] percentage points from baseline [$P < 0.0001$], compared with a mean absolute change of 0.0 [2.0] percentage points in subjects who received placebo [$P = 0.9943$]).

The dose-response relationship of VX-445 in TC was assessed for ppFEV₁ and SwCl for F/MF patients using population-PK/PD modeling. Results indicate that a dose of 200 mg qd provides meaningful improvement for ppFEV₁ and SwCl, while a dose less than 200 mg qd may result in some subjects having suboptimal improvement in CFTR function. No differences in the safety profile of VX-445/TEZ/IVA were observed across the doses.

TEZ and IVA Dosages

TEZ will be administered as 100 mg qd and IVA will be administered as 150 mg q12h. This is the approved dosing regimen for Symdeko, which is approved in certain countries.

Dosage for Subjects Aged 12 to 17 Years

Phase 3 studies with IVA and TEZ/IVA have demonstrated similar exposures between adults (≥ 18 years old) and adolescent subjects ≥ 12 to < 18 years of age. Significant differences in VX-445, TEZ, and IVA exposures are not expected between adolescent subjects and adults in the present study; therefore, all subjects will receive the same dose of VX-445/TEZ/IVA.

9.3.3 Rationale for Study Population

This study will enroll subjects with CF with F/MF genotypes. As described in [Section 5.2](#), patients with F/MF genotypes have unmet need and are expected to respond to a TC regimen of VX-445/TEZ/IVA based on results from a Phase 2 study conducted in F/MF subjects, in vitro experiments in relevant human F/MF cell-based model systems, and results from ongoing Phase 2 studies with VX-445/TEZ/IVA.

Given the progressive nature of CF, there is a strong rationale for treating patients earlier in life. Experience with CFTR modulators in adolescent subjects ≥ 12 to < 18 years of age, including with TEZ/IVA, suggests that the exposures and safety profile of VX-445/TEZ/IVA will be similar in adolescents and adults, which supports evaluation of VX-445/TEZ/IVA in adolescents in the present study.

9.3.4 Rationale for Study Assessments

The PD and efficacy endpoints being evaluated (SwCl, spirometry, PEx, anthropometric measurements, and patient-reported outcomes) are widely accepted and generally recognized as reliable, accurate, and relevant to the study of individuals with CF. SwCl was evaluated in the registration study of IVA (Kalydeco), and spirometry and CFQ-R assessments were evaluated in the registration studies of IVA (Kalydeco) and LUM/IVA combination therapy (Orkambi).

[REDACTED]

[REDACTED]

[REDACTED]

9.4 Study Restrictions

9.4.1 Prohibited Medications

Table 9-2 lists prohibited medications. A non-exhaustive list of study prohibitions and cautions for medication will be provided in the Study Reference Manual.

Table 9-2 Prohibited Medications

Medication	Timing of Restriction		Rationale
	Start of Restriction	End of Restriction	
Moderate and strong CYP3A inducers	None allowed within 14 days before the first dose of the study drug on Day 1	None allowed through completion of study participation	VX-445, TEZ, and IVA are metabolized extensively via CYP3A4. Therefore, use of moderate and strong inducers and inhibitors of CYP3A, which have the potential to alter the exposure of VX-445, TEZ, or IVA, will be prohibited.
Moderate and strong CYP3A inhibitors (except ciprofloxacin) ^a	None allowed within 14 days before the first dose of the study drug on Day 1	None allowed through completion of study participation	
Sensitive OATP1B1 substrates	None allowed within 14 days before the first dose of the study drug on Day 1	None allowed through completion of study participation	VX-445 is a potential inhibitor of the hepatic transporter OATP1B1. Therefore, sensitive substrates of OATP1B1, such as HMG-CoA reductase inhibitors (“statins”) are prohibited during treatment.
CFTR modulators (investigational or approved), except for study drugs	None allowed within 28 days before the first dose of the study drug on Day 1	None allowed until after the last dose of study drug	These agents may confound the results of this study.

CYP: cytochrome P450; IVA: ivacaftor; OATP1B1: organic anion transporting polypeptide 1B1; TEZ: tezacaftor

^a Ciprofloxacin is not a moderate CYP3A inhibitor on the basis of results of a drug-drug interaction study conducted with IVA, a sensitive CYP3A substrate (Kalydeco [ivacaftor] US Package Insert).

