9.5 Prior and Concomitant Medications

Information regarding prior and concomitant medications, including CF medications, other medications, and herbal and naturopathic remedies, will be collected from each subject’s source documentation for medications taken within 56 days before the Screening Visit through completion of study participation, as defined in [Section 9.1.6](#).

For subjects who are screened but are not subsequently randomized, details of prior medication will be documented only in the subjects’ source documents.

- Subjects should remain on a stable treatment regimen for their CF from 28 days before the Day 1 Visit through completion of study participation. Stable treatment regimen is defined as the current treatment regimen for CF that subjects have been following for at least 28 days before the Day 1 Visit. Subjects should not initiate long-term treatment with new medication from 28 days before the Day 1 Visit through completion of study participation. Guidelines for stable treatment regimens for CF are as follows:
 - o Subjects who are taking inhaled tobramycin or other chronically inhaled antibiotics should remain on that regimen throughout the study.
 - o Subjects who cycle onto and off of an inhaled antibiotic should continue on their prior schedule. The timing of the first dose of study drug on the Day 1 Visit should be synchronized as closely as possible (e.g., not more than ± 3 days) to the first day in the cycle onto the inhaled antibiotic.

- o Subjects who alternate between 2 different inhaled antibiotics should remain on the same cycling schedule during the study. The timing of the first dose of study drug on the Day 1 Visit should be synchronized as closely as possible (e.g., not more than ± 3 days) to the first day in the cycle onto 1 of the inhaled antibiotics.
- Subjects may receive doses of prednisone or prednisolone of up to 10 mg/day chronically, or up to 60 mg daily for up to 5 days.
- Information about bronchodilator use during the study will be collected and documented. Subjects who are using a bronchodilator must have their spirometry assessments performed according to the guidelines provided in [Section 11.6.1](#).

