9.9 Removal of Subjects

Subjects may withdraw from the study at any time at their own request. Subjects may be withdrawn from study drug treatment at any time at the discretion of the investigator or Vertex for safety, behavior, noncompliance with study procedures, or administrative reasons. If a subject has been withdrawn from study drug treatment, the subject will continue to be followed, provided that the subject has not withdrawn consent (and assent, as applicable).

In addition, a subject must be discontinued from study drug treatment if the subject meets any of the following criteria:

- Has a screening *CFTR* genotype that does not confirm study eligibility if a previous *CFTR* genotype laboratory report was used to establish eligibility. These subjects must be discontinued from the study ([Section 8.1](#))
- Meets any of the stopping (discontinuation) criteria ([Section 9.8](#))
- Becomes pregnant ([Section 11.7.7.2](#))

Subjects who discontinue study drug treatment should return for study assessments, as noted in [Section 9.1.3](#).

If a subject does not return for a scheduled visit, reasonable effort will be made to contact the subject. In any circumstance, reasonable effort will be made to document subject outcome. The investigator will inquire about the reason for withdrawal, request that the subject return all unused investigational product(s), request that the subject return for an ETT Visit and Safety Follow-up Visit, if applicable (see [Section 9.1.3](#)), and follow up with the subject regarding any unresolved AEs.

If the subject withdraws consent or assent for the study, no further assessments will be performed. Vertex may retain and continue using the study data and samples after the study is over, and may use the samples and information in the development of the study compound, and for other drugs and diagnostics, in publications and presentations, and for education purposes. If the subject withdraws from the study, the study data and samples collected will remain part of the study. A subject will not be able to request the withdrawal of his/her information from the study data. A subject may request destruction of the samples collected from him/her during the study as long as those samples can be identified as his/her samples.

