13.2.3 Investigator Compliance

No modifications to the protocol will be made without the approval of both the investigator and Vertex. Changes that significantly affect the safety of the subjects, the scope of the investigation, or the scientific quality of the study (i.e., efficacy assessments) will require IRB/IEC notification before implementation, except where the modification is necessary to eliminate an apparent immediate hazard to human subjects. Vertex will submit all protocol modifications to the required regulatory authorities.

When circumstances require an immediate departure from procedures set forth in the protocol, the investigator will contact Vertex to discuss the planned course of action. If possible, contact will be made before the implementation of any changes. Any departures from the protocol will be fully documented in the source documentation and in a protocol deviation log.

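### Table 9-2 keeps three interaction-based medication bans in force to Week 24 or later for subjects who have permanently stopped study drug (minor, cheap to fix)

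*Protocol*

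**What the plan says.** **The ban.** Protocol Table 9-2 ends the restriction in each of its first three rows with "None allowed through completion of study participation". The reason given for the two CYP3A rows is that such agents may alter exposure to VX-445, TEZ or IVA. The reason for the third row is that VX-445 may inhibit OATP1B1, so that sensitive substrates such as statins "are prohibited during treatment". The fourth row, CFTR modulators, is justified by possible confounding of results and is released after the last dose.

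**Who stays under it.** Section 9.1.4: "Subjects who prematurely discontinue study drug treatment will continue to complete all scheduled study visits for assessments". Section 9.9: "If a subject has been withdrawn from study drug treatment, the subject will continue to be followed", provided consent stands. For these subjects Section 9.1.6 defines the end of participation as "the latest of the Week 24 Visit, ETT Visit, or Safety Follow-up Visit (if required").

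**Neighbouring rules.** Criterion 8 of Section 8.1 requires subjects to be "Willing to remain on a stable CF treatment regimen" to the same end point. Within its bullet on the stable CF regimen, Section 9.5 says: "Subjects should not initiate long-term treatment with new medication from 28 days before the Day 1 Visit through completion of study participation". Section 13.2.3 says: "Any departures from the protocol will be fully documented in the source documentation and in a protocol deviation log". SAP Appendix D names the need for a prohibited medicine among the reasons for stopping treatment.

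**The concern.** The end date and the reasons for it do not match. An inducer or inhibitor of CYP3A cannot alter exposure to a drug that has cleared, and VX-445 cannot inhibit a transporter once it is gone. In the OATP1B1 row the rationale stops with treatment while the end cell runs on to the end of participation.

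The awkward case is the one that SAP Appendix D foresees. A subject stops study drug because a prohibited medicine is needed, agrees to remain in follow-up, and on the wording of Table 9-2 is still barred from that medicine until Week 24 or later. At stake are the care of subjects who are off drug, avoidable logged departures and, possibly, willingness to stay in follow-up. The effect on retention is inference; nothing in the documents quantifies it.

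**Working it through.** The plan states no figure for this point, so there is none to reproduce. The check is date arithmetic plus a comparison of sections.

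**Inputs**
- Week 24 target day: 169 (SAP Table 12-1), with a visit window of ±5 days (Protocol Table 3-2), so Day 164 to 174.
- Safety Follow-up Visit: 28 ± 7 days after the last dose (Protocol Table 3-2).
- Washout after the last dose: not in the documents. Assumed 28 days, with a range of 14 to 42.

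**Formulas** (target days; the ETT Visit is taken to fall soon after stopping and so not to set the end date)
- End of ban = later of Day 169 and (last dose + 28).
- Days barred = end of ban − last dose.
- Excess = days barred − washout, not below 0.

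| Last dose | Last dose + 28 | End of ban | Days barred | Excess, washout 14 / 28 / 42 |
|---|---|---|---|---|
| Day 15 | 43 | 169 | 154 | 140 / 126 / 112 |
| Day 29 | 57 | 169 | 140 | 126 / 112 / 98 |
| Day 85 | 113 | 169 | 84 | 70 / 56 / 42 |
| Day 141 | 169 | 169 | 28 | 14 / 0 / 0 |
| Day 155 | 183 | 183 | 28 | 14 / 0 / 0 |

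With the Week 24 window, Day 29 gives 164 − 29 = 135 to 174 − 29 = 145 days, and Day 85 gives 79 to 89. From a last dose on Day 141 onward the Safety Follow-up Visit can set the end date. At its latest it falls 28 + 7 = 35 days after the last dose, which is 35 − 28 = 7 days beyond a 28-day washout. The problem therefore belongs to early stoppers.

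**Comparison of sections**
1. All three rationales need study drug to be present. None mentions protecting data collected off drug.
2. The only row justified by confounding, CFTR modulators, is the one released after the last dose. That makes it hard to read the longer ban as protection of off-drug data, and it shows that an end date tied to the last dose can be run in this trial.
3. No section exempts subjects who are permanently off drug. Those who withdraw consent or are lost to follow-up leave the ban earlier, because Section 9.1.6 ends their participation on the withdrawal or last-contact date.
4. Under SAP Section 9.2.4, a medicine started after the treatment-emergent period (which ends no later than 28 days after the last dose) is a post-treatment medication. The example in SAP Section 9.2.7 concerns prohibited concomitant medication, so late use off drug does not fit it directly, although that list is not exhaustive.

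**The case against.** **Little is at stake.** This stands. Section 13.2.3 gives a route: when an immediate departure is needed, the investigator contacts the sponsor and the departure is recorded. A reader might infer that the protocol forces a needed medicine to be withheld, or the subject to be removed. No section says either.

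**A single end date is simple and may have a purpose.** It could mirror the stable-CF-regimen rule, or avoid a fresh washout before the open-label study. Neither reason appears in the documents, and the open-label eligibility rules are not in them.

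**Residual drug justifies some time after the last dose.** This stands, and it is why the end date should include a washout. The documents give no half-life, so the 28 days, borrowed from the treatment-emergent period, has no pharmacological source here. The 140 and 84 days barred do not depend on it; the excess figures do.

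**Rechallenge.** This stands too. Section 9.8.1 allows study drug to resume after a transaminase interruption, whatever its length. An end date tied simply to the last dose could be misread during a long interruption, so the wording must refer to permanent discontinuation.

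**Section 9.5.** A reader might infer that it separately bars any new long-term medicine, so that changing Table 9-2 alone would achieve little. The sentence is not expressly limited to CF medicines, but it sits between the definition of a stable CF regimen and the guidelines for one, and its natural reading is CF therapy. A clarification would help but is not essential.

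**Conclusion.** The point holds as a minor, inexpensive improvement. For a subject permanently off study drug but still followed, the first three rows of Table 9-2 outlast their own stated reasons: 140 days barred after a last dose on Day 29 and 84 after Day 85, of which 112 and 56 lie beyond an assumed 28-day washout (126 to 98 and 70 to 42 for washouts of 14 to 42 days). The documents do not give the number of subjects affected.

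Two stronger conclusions are not supported. One is that every off-drug use becomes an important protocol deviation: SAP Section 9.2.7 leaves that to a blinded team, which applies it only where data or the subject's rights, safety or well-being could be significantly affected. The other is that trial results are compromised: no efficacy analysis, power or alpha figure depends on this end date, and the Week 4 primary endpoint is not materially touched.

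**What to change.** In the first three rows of Table 9-2, change the end of restriction to:

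> None allowed until [washout set by clinical pharmacology, e.g. 28 days] after the last dose following completion or permanent discontinuation of study drug, or completion of study participation, whichever is earlier. The restriction continues during any temporary interruption.

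Optionally, state in Section 9.5 that the bar on new long-term medication refers to CF therapy. The stable-CF-regimen rule and the CFTR-modulator row stay as they are.

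**Cost.** Three table cells, and one sentence if Section 9.5 is clarified, in any amendment. For subjects who complete treatment and do not enter the open-label study, a 28-day washout shortens the ban by at most 35 − 28 = 7 days (35 − 14 = 21 days with a 14-day washout). For those who enter it within 28 days of the Week 24 Visit, participation already ends at Week 24 and a 28-day washout changes nothing. The downside is that some off-drug subjects may take these medicines during follow-up. Section 9.5 already collects medications through the end of participation, so that use would be recorded.
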